- Absence of signs and symptoms (including worsening laboratory values) indicating disease progression
- No decline in ECOG performance status
- Absence of rapid progression of disease or of progressive disease at critical anatomical sites (eg, cord compression) requiring urgent alternative medical intervention

Study treatment may continue under the following circumstances after repeat/confirmatory imaging (≥ 4 weeks after initial scan showing PD):

- If repeat imaging shows $< 20\%$ tumor burden increase compared to nadir, stable or improved previous new lesion (if identified as cause for initial PD), and stable/improved non-target disease (if identified as cause for initial PD), treatment may be continued and/or resumed (PD is not confirmed).
- If repeat imaging confirms PD due to any of the scenarios listed below, subjects will be discontinued from study therapy with the following exception: if the subject is achieving a clinically meaningful benefit, and there is no further increase in the tumor burden at the confirmatory tumor imaging compared to the initial PD assessment, an exception to continue treatment may be considered following consultation with the Sponsor. In this case, if treatment is continued, tumor imaging should continue to be performed at the protocol specified intervals.

In determining whether or not the tumor burden has increased or decreased, site study team should consider all target lesions as well as non-target lesions.

If repeat imaging shows an objective response or stable disease relative to nadir, treatment with study medication may continue and subjects will return to regular scheduled imaging every 8 weeks starting with the next protocol-specified imaging time-point. Subjects who obtain a confirmatory scan do not need to undergo scheduled imaging assessment ≤ 2 weeks later (eg, if a subject obtains a scan at Week 14 to confirm a Week 8 PD and progression is not confirmed, they will not also be required to complete the scheduled Week 16 scan).

Progressive Disease is confirmed at repeat imaging if:

- Tumor burden remains $\geq 20\%$ (and at least 5 mm absolute increase) compared to nadir
- Non-target disease resulting in initial PD is worse (qualitative)
- New lesion(s) resulting in initial PD is worse (qualitative)
- Additional new lesion(s) since last evaluation

If repeat imaging confirms PD, subjects will be discontinued from study therapy.

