8.10. Sample Size

Assuming the ORR for subjects treated with nivolumab alone is 25%, 120 subjects in total are needed to detect an improvement of 20% in ORR for subjects treated with andecaliximab and nivolumab with approximately 83% power at one-sided significance level of 10% using a CMH test. The assumption of nivolumab ORR is based on the upper bound of the 95% CI of the estimated ORR in CheckMate-032 Study {Le 2016}.

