6.1. Primary Efficacy Endpoint

The primary efficacy endpoint of this study is objective response rate (ORR), defined as the proportion of subjects with best overall response of complete response (CR) or partial response (PR) after starting study drug but before starting any new chemotherapy or radiotherapy based on revised RECIST 1.1.

As sensitivity analysis, confirmed ORR, defined as the proportion of subjects with best overall response of confirmed CR or confirmed partial response (PR) after starting study drug but before starting any new anti-cancer therapy based on revised RECIST 1.1, will also be analyzed. The confirmatory response is required at least 4-week later after the initial CR/PR for confirmed ORR.

Overall response for each visit is derived in the following process. The rules should be applied by the order listed below.

- Response assessments occurring after new anticancer therapy (including radiation therapy), after missing two previous consecutive tumor scans, or after confirmed progressive disease (PD) will not be included for ORR analysis.
- If overall response for the first time point of a visit is an imaging PD, in order to differentiate “pseudo-progression (pseudo-PD)” from “definitive progression”, the first imaging PD requires confirmation either by another imaging PD at the confirmatory visit at least 4 weeks apart or by the subsequent clinical PD/ radiation therapy. The first imaging PD will be considered as “confirmed PD” by any of the following:
 - The overall response at the confirmatory visit is also PD;
 - No more tumor assessment is available that is 4 weeks apart;
 - The overall response at the confirmatory visit is non-evaluable (NE) and no more tumor assessments follow the confirmatory visit;
 - First imaging PD is followed by subsequent clinical PD or radiation therapy.

Otherwise, the first imaging PD will be “Pseudo PD”.

- Both clinical PD and radiation therapy are considered as PD, and no confirmation is required.

The best overall response for each subject across the time points is derived based on the rank CR > PR > SD > pseudo-PD > PD (including clinical PD, confirmed imaging PD, and radiation therapy) > NE.

For confirmed overall response for each visit, in addition to the rules listed above, the following rules should also be applied.

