- If overall response of a visit is CR or PR, a confirmatory visit at least 4 weeks later is required. Overall response for the visit is derived based on overall response at the first time point and overall response at the confirmatory visit.
- If overall response of a visit is SD/NE, no confirmatory visit is required and the overall response for the visit is SD/NE correspondingly.

The rule for deriving confirmed overall response at each visit is specified in [Table 5](#). The best confirmed overall response for each subject across the time points is derived based on the rank CR confirmed > PR confirmed > CR not confirmed > PR not confirmed > SD > pseudo-PD > PD (including clinical PD, confirmed imaging PD, and radiation therapy) > NE.

Table 5. Confirmed Overall Response Derivation

Overall Response at First Visit	Overall Response at Confirmatory Visit	Overall Response for the Time Point	Date of Response
CR	CR	CR confirmed	First visit
	Responses other than CR or there is no confirmatory visit	CR not confirmed	First visit
PR	CR/PR	PR confirmed	First visit
	Responses other than CR/PR or there is no confirmatory visit	PR not confirmed	First visit
PD	PD/ clinical PD/ radiation therapy, or there is no confirmatory visit	PD	First visit
	NE	PD	First visit
	Responses other than PD/clinical PD/ radiation therapy/NE	pseudo-PD	First Visit
NE	Not required	NE	First visit
SD	Not required	SD	First visit

Note: Response after treatment discontinuation does not need to be confirmed.

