6.2. Secondary Efficacy Endpoint

6.2.1. Progression-Free Survival

Progression free survival (PFS), defined as the interval from the date of randomization to the earlier of the first definitive PD (as defined in Section 6.2.1) or death from any cause. The first definitive PD is defined as the first radiation therapy, the first clinical PD, and the first confirmed imaging PD, whichever comes first. Pseudo-PD will not be considered as definitive PD.

Data will be censored on the date of last adequate tumor assessment for subjects (including assessments with a NE outcome):

- who do not have definitive PD or die before study discontinuation, or
- who start new anticancer therapy prior (radiation therapy excluded) to definitive PD or death, or
- who have ≥ 2 consecutive missing tumor assessments before definitive PD or death.

Subjects without any adequate baseline tumor assessment are censored on the randomization date. The adequate baseline tumor assessment is defined as the window from (randomization date - 35 days) to randomization date.

PFS in months will be calculated as $(\text{date of event/censoring} - \text{date of randomization} + 1) / 30.4375$.

Survival function of PFS is estimated using Kaplan-Meier method and compared using the log-rank test stratified by PD-L1 status at screening. PFS rates at 1, 2, 3, 6, 9, 12 months, and the median with 95% CIs will be derived using Kaplan-Meier methods by treatment arm. Kaplan-Meier curves will also be provided. In addition, hazard ratio (HR) and corresponding 95% CI will be estimated for PFS using the Cox proportional hazards regression model stratified by PD-L1 status at screening.

Follow-up time in months for PFS will be summarized as a continuous variable with descriptive statistics.

- For a subject who is censored from PFS and has discontinued from tumor assessment, duration of PFS follow-up = $(\text{Date of Censoring} - \text{randomization date} + 1) / 30.4375$
- For subjects with a definitive PFS event and censored subject with ongoing tumor assessment, duration of PFS follow-up = $(\text{Date of last tumor assessment in the database} - \text{randomization date} + 1) / 30.4375$

For subjects who have imaging examinations on various dates that are nevertheless assigned to the same nominal visit, the following rules apply for the calculation of the endpoint date:

- The response date will be the last date associated with that particular imaging time point.

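### SAP 6.1: read literally, the fourth PD-confirmation condition overrides a repeat scan that disproved progression and back-dates the PFS event, against Table 5 and Protocol 6.2.9.1

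*SAP*

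**What the plan says.** **SAP 6.1, rules for overall response at each visit.** These are to be applied in the order listed.

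- The first rule removes response assessments that come after new anticancer therapy, after two consecutive missed scans, "or after confirmed progressive disease (PD) will not be included for ORR analysis".
- The second rule defines confirmation. A first imaging PD is confirmed if any of four conditions is met: PD at the confirmatory visit; no later scan 4 weeks apart; NE at the confirmatory visit with no scan after it; or "First imaging PD is followed by subsequent clinical PD or radiation therapy". Pseudo-PD is what remains when none applies.
- Clinical PD and radiotherapy also count as PD in their own right, without confirmation.

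**SAP Table 5.** When the first visit shows PD and the confirmatory-visit column reads "Responses other than PD/clinical PD/ radiation therapy/NE", the time point is pseudo-PD. The table is written for confirmed ORR, and its rules are added to those above.

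**SAP 6.2.1 (PFS).** "The first definitive PD is defined as the first radiation therapy, the first clinical PD, and the first confirmed imaging PD, whichever comes first". Pseudo-PD is not an event. SAP 6.2.3 uses the same definition for DOR.

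**Protocol 6.2.9.1.** If the repeat scan meets its non-progression criteria, "treatment may be continued and/or resumed (PD is not confirmed".

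**The concern.** The confirmation step exists to separate pseudo-progression from definitive progression. The third condition has a guard, since no scan may follow the NE visit. The fourth has none: it sets no window and does not ask whether a CR, PR or SD scan came in between. A scan disproved at Week 12 can therefore be declared true progression by a clinical event many months later.

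The late event does not need this condition in order to count. SAP 6.1 and 6.2.1 already make clinical PD and radiotherapy progression events on their own dates, and Protocol 5.4.2 counts palliative radiotherapy as clinical progression for PFS. What the condition adds in these subjects is back-dating.

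At stake are the PFS date, the DOR and, under one order of the rules, responder status. Classification would depend on an event after the response, so it could change from one data cut to the next. Two programmers could also derive different datasets from the bullets and from Table 5.

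**Working it through.** **Design figure.** The plan gives no number for this rule. The nearest design figure is in Protocol 8.10: 25% versus 45% ORR, "approximately 83% power at one-sided significance level of 10% using a CMH test", with 60 per arm (Protocol 3.2). Using the log odds ratio:

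- OR = (0.45/0.55)/(0.25/0.75) = 2.45, with natural log 0.898.
- SE = √[1/(60×0.45×0.55) + 1/(60×0.25×0.75)] = 0.395.
- Power = Φ(0.898/0.395 − 1.2816) = 83.9%.

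Fisher's exact test by enumeration gives 81.1%. The stated figure reproduces, and the rule examined here is not an input to it.

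**Illustrative subject (assumed, not from the documents).** Randomised and first dosed on Day 1. Imaging PD on Day 57 (Week 8: 7×8+1). PR on the repeat scan on Day 85 (57+28). PR on later scans. Clinical PD on Day 337 (Week 48: 7×48+1).

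**Applying the four conditions to the Day 57 PD.**

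1. PD at the confirmatory visit: no, it was PR.
2. No later scan 4 weeks apart: no, there are several.
3. NE with nothing after it: no.
4. Later clinical PD or radiotherapy: yes, on Day 337.

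One condition is enough, so the bullets give confirmed PD on Day 57. Table 5 gives pseudo-PD, because the confirmatory visit was PR.

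**Consequences.** SAP 6.2.1: PFS = (event date − randomisation date + 1)/30.4375. SAP 6.2.3: DOR = (event date − first response date + 1)/30.4375.

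| | Bullets; exclusion applied once PD status is set | Bullets; exclusion applied first, as listed | Table 5 reading |
|---|---|---|---|
| Day 57 scan | confirmed PD | confirmed PD | pseudo-PD |
| PFS | 57/30.4375 = 1.87 months | 1.87 months | 337/30.4375 = 11.07 months |
| Best response | PD, non-responder | PR, responder | PR, responder |
| DOR | none | (57−85+1)/30.4375 = −0.89 months | (337−85+1)/30.4375 = 8.31 months |

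In the middle column nothing has yet been labelled confirmed PD when the exclusion runs, so the later PRs stay and rank above PD. The PFS event then precedes the response. PFS is shortened by 280/30.4375 = 9.20 months under either order.

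**Contrast case.** Suppose the Day 337 progression is instead seen on a scan and counted as confirmed, with no clinical PD or radiotherapy recorded at any time. The fourth condition is never met, the Day 57 scan stays pseudo-PD, PFS is 11.07 months and the PR counts. The same disease course is thus classified differently according to how the final progression was detected.

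**The case against.** The strongest reply is that a narrower rule was meant. Table 5 places clinical PD and radiotherapy in the confirmatory-visit column, as if they stood in for a repeat scan, and SAP Table 4 pairs each scan with its own confirmatory visit. This is plausible and may well be the intent. It does not settle the text: Table 5 serves confirmed ORR and is added to the bullets, and nothing restricts the fourth condition for ORR or PFS.

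A reader might infer several stronger conclusions that the documents do not support:

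- *That responders are certainly lost.* This holds only if the exclusion is applied after PD status is set, although it is listed first. Subjects with a CR or PR before the first imaging PD keep it, and those whose best later response is SD are non-responders on any reading.
- *That pseudo-progressors in general are affected.* Only those with later clinical PD or radiotherapy are, and Protocol 5.4.2 allows on-study radiotherapy only exceptionally.
- *That ORR shifts by a stated number of points, or that one arm is favoured.* The trial is open-label and uses investigator assessment, so a difference between arms is possible. The documents give neither the frequency of these sequences nor their split by arm.
- *That the primary test is compromised.* SAP 2.3 and 6 make the updated p-values display-only, and SAP 1 and 6 base the CSR's efficacy results on the primary analysis. The SAP governing that analysis was not supplied.

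**Conclusion.** The point stands as a rule that is wrong as written and contradicts the SAP's own table and Protocol 6.2.9.1. The firm consequence is in PFS: under the literal bullets the event is dated to a scan already disproved, 1.87 instead of 11.07 months in the illustrative subject. The effect on response is conditional: non-responder if the exclusion follows PD status, or responder with a DOR of −0.89 months if it runs first. Neither outcome is acceptable.

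The per-subject figures rest on the assumed dates. The number of subjects affected and any imbalance between arms cannot be determined, so no ORR-point effect should be quoted. For the document supplied, the consequence is limited to display-only updated analyses. It would be larger if the primary-analysis SAP carries the same condition, which only the sponsor can check.

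**What to change.** 1. Reword the fourth condition along these lines: *Clinical PD or radiotherapy confirms a first imaging PD only if it occurs before any tumour assessment, at least 4 weeks after that scan, with a response other than PD or NE.*
2. Add: *Once a confirmatory assessment shows CR, PR or SD, the first imaging PD remains pseudo-PD; any later clinical PD or radiotherapy is a new PD with its own date.*
3. State that confirmation status is derived before assessments after confirmed PD are excluded.
4. Use the same derivation for ORR, confirmed ORR, PFS and DOR.
5. Check the primary-analysis SAP and its programs for the same condition.

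The cost is two sentences on confirmation, a statement of rule order, and matching program logic, with no new data. These are analysis derivation rules only and change no treatment decision.

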6.1.1. Statistical Hypothesis for the Primary Efficacy Endpoint

The primary efficacy hypothesis is that there is no difference between Treatment Group (Group T) and Control Group (Group C) in ORR. Using R_T and R_C to denote the objective response rate of Treatment Group (Group T) and Control Group (Group C), respectively, the statistical hypotheses to be tested in this study will be:

$$H_0: R_T = R_C$$

$H_1: R_T > R_C$ (Group T is superior to Group C in terms of ORR)

6.1.2. Analysis for the Primary Efficacy Endpoint

The ORR endpoint will be tested at a two-sided alpha level of 0.2. The ORR will be presented with corresponding 2-sided 80% and 95% exact confidence intervals (CIs) calculated using the Clopper-Pearson method. Odds ratio will also be presented with corresponding 80% and 95% CIs be calculated using the exact CMH Chi-square test stratified by screening PD-L1 status. Subjects who do not have sufficient baseline or on-study tumor assessments to characterize response will be counted as non-responders and included in the denominator only.

In addition, the confirmed ORR, defined as the proportion of subjects with best overall response of confirmed CR/confirmed PR will also be presented as a sensitivity analysis. The same analysis methods as for ORR mentioned above will be applied for confirmed ORR.

The analysis for the ORR and confirmed ORR will be performed based on the ITT Analysis Set.

6.2. Secondary Efficacy Endpoint

6.2.1. Progression-Free Survival

Progression free survival (PFS), defined as the interval from the date of randomization to the earlier of the first definitive PD (as defined in Section 6.2.1) or death from any cause. The first definitive PD is defined as the first radiation therapy, the first clinical PD, and the first confirmed imaging PD, whichever comes first. Pseudo-PD will not be considered as definitive PD.

Data will be censored on the date of last adequate tumor assessment for subjects (including assessments with a NE outcome):

- who do not have definitive PD or die before study discontinuation, or
- who start new anticancer therapy prior (radiation therapy excluded) to definitive PD or death, or
- who have ≥ 2 consecutive missing tumor assessments before definitive PD or death.

Subjects without any adequate baseline tumor assessment are censored on the randomization date. The adequate baseline tumor assessment is defined as the window from (randomization date - 35 days) to randomization date.

PFS in months will be calculated as $(\text{date of event/censoring} - \text{date of randomization} + 1) / 30.4375$.

Survival function of PFS is estimated using Kaplan-Meier method and compared using the log-rank test stratified by PD-L1 status at screening. PFS rates at 1, 2, 3, 6, 9, 12 months, and the median with 95% CIs will be derived using Kaplan-Meier methods by treatment arm. Kaplan-Meier curves will also be provided. In addition, hazard ratio (HR) and corresponding 95% CI will be estimated for PFS using the Cox proportional hazards regression model stratified by PD-L1 status at screening.

Follow-up time in months for PFS will be summarized as a continuous variable with descriptive statistics.

- For a subject who is censored from PFS and has discontinued from tumor assessment, duration of PFS follow-up = $(\text{Date of Censoring} - \text{randomization date} + 1) / 30.4375$
- For subjects with a definitive PFS event and censored subject with ongoing tumor assessment, duration of PFS follow-up = $(\text{Date of last tumor assessment in the database} - \text{randomization date} + 1) / 30.4375$

For subjects who have imaging examinations on various dates that are nevertheless assigned to the same nominal visit, the following rules apply for the calculation of the endpoint date:

- The response date will be the last date associated with that particular imaging time point.
- The progression date will be the first date associated with that particular imaging time point.

Incomplete or missing dates of initiation of anticancer therapy other than the study treatment are imputed as follows:

- If the day is missing but the month and year are available, then the imputed day will be the last day of the month.
- If day and month are missing but year is available, then the imputed day and month will be 01Jan or the last day of the month for the last adequate disease assessment if they have the same year, whichever is later.

The analysis of PFS will be performed based on the ITT Analysis Set.

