6.2.9.2. Tumor Imaging

Contrast-enhanced CT (without contrast if use of contrast is contraindicated) or gadolinium-enhanced MRI of the chest, abdomen, and pelvis will be performed at screening, every 8 weeks during the study and at the EOS visit if one has not been performed within the last 8 weeks. CT is the preferred imaging modality for this study. Tumor burden will be evaluated solely based on radiographic imaging per RECIST v 1.1, with the modifications noted in Section 6.2.9.1. Chest x-ray, ultrasound, endoscopy, laparoscopy, positron-emission tomography, radionuclide scans, or tumor markers will not be considered for response assessment.

For radiographic evaluations, it is recommended that the same method of assessment and the same technique (eg, scan type, scanner, subject position, dose of contrast, injection/scan interval) should be used to characterize each identified and reported lesion at baseline and during study treatment and follow-up. Local site study team reading (investigator assessment with site radiology reading) based on RECIST 1.1 will be used to determine subject eligibility.

Scans taken as part of standard medical practice up to 28 days prior to randomization can be used for Screening as long as they are of diagnostic quality and meet all study requirements. During the treatment phase, scans may be performed at time points other than every 8 weeks as clinically indicated to assess tumor progression.

For subjects who stop study treatment in the absence of disease progression (eg, experienced unexpected toxicity), scans should continue to be collected approximately every 8 weeks until disease progression or initiation of systemic anti-tumor therapy other than the study treatment, whichever is earlier.

All relevant clinical and radiographic information required to make each assessment must be made available for source verification and submission to a central reader. CCI [REDACTED] Disease progression will be determined by the investigator or qualified designee.

Imaging should be continued at protocol-specified intervals until whichever of the following occurs first:

- Initial site-assessed disease progression is confirmed
- The start of new anti-cancer treatment
- Withdrawal of consent
- Death
- The end of the study

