8.3. Data Handling Conventions

By-subject listings will be created for important variables from each eCRF module. Summary tables for continuous variables will contain the following statistics: N (number in population), n (number with data), mean, standard deviation, 95% confidence intervals (CIs) on the mean, median, minimum, and maximum. Summary tables for categorical variables will include: N, n, percentage, and 95% CIs on the percentage. Unless otherwise indicated, 95% CIs for binary variables will be calculated using the binomial distribution (exact method) and will be 2 sided. Data will be described and summarized by dose level/cohort, analysis set, and time point. As appropriate, changes from baseline to each subsequent time point will be described and summarized. Similarly, as appropriate, the best change from baseline during the study will also be described and summarized. Graphical techniques (eg, waterfall plots, Kaplan-Meier [KM] curves, line plots) may be used when such methods are appropriate and informative.

The baseline value used in each analysis will be the last (most recent) pretreatment value. Data from all sites will be pooled for all analyses. Analyses will be based upon the observed data unless methods for handling missing data are specified. If there is a significant degree of non-normality, analyses may be performed on log-transformed data or nonparametric tests may be applied, as appropriate.

The following censoring conventions will be applied to tumor control endpoints:

- PFS: Data from surviving, non-progressing subjects will be censored at the earliest of the time of initiation of antitumor treatment other than the study treatment or the last time that lack of definitive progression was objectively documented. Data from subjects who have disease progression or die after ≥ 2 consecutive missing or inadequate tumor assessments will be censored at the last time prior to the missing assessments that lack of definitive disease progression was objectively documented.
- OS: Data from surviving subjects will be censored at the last time that the subject was known to be alive.

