3.8.2. Analysis Visit Windows

Subject visits might not occur on protocol-specified days. Therefore, for the purpose of analysis, observations will be assigned to analysis windows.

The analysis windows for chemistry, hematology and vital signs are provided in [Table 1](#). The analysis windows for urinalysis, pregnancy test, ECG, and ECOG are provided in [Table 2](#). The analysis windows for Thyroid Function Tests (TSH, T3, and free T4) are provided in [Table 3](#). The analysis windows for tumor assessments are provided in [Table 4](#).

Table 1. Analysis Visit Windows for Chemistry, Hematology and Vital Signs

Analysis Visit	Study Day	Lower Limit (inclusive)	Upper Limit (inclusive)
Baseline	1	-28	1 (before 1 st dose)
Week 2	15	1 (after first dose)	21
Week 4	29	22	35
Week 6	43	36	49
Week X=8, 10, ...	7*x+1	7x-6	7*x + 7
Safety Follow-up		max (andecaliximab end date, Nivo end date) + 1	max(andecaliximab end date + 30 days, Nivo end date + 5 months)

Table 2. Analysis Visit Windows for Urinalysis, Pregnancy Test, ECG, and ECOG

Analysis Visit	Study Day	Lower Limit (inclusive)	Upper Limit (inclusive)
Baseline	1	-28	1 (before 1 st dose)
Week 4	29	1 (after first dose)	42
Week 8	57	43	70
Week 12	85	71	98
Week X=16, 20, ...	7*x+1	7x-13	7*x + 14
Safety Follow-up		max (andecaliximab end date, Nivo end date) + 1	max(andecaliximab end date + 30 days, Nivo end date + 5 months)

Note. For pregnancy test, use results from serum test for screening and results from urine test for post-screening visit.

Table 3. Analysis Visit Windows for Thyroid Function Tests (TSH, T3, free T4)

Analysis Visit	Study Day	Lower Limit (inclusive)	Upper Limit (inclusive)
Baseline	1	-28	1 (before 1 st dose)
Week 8	57	1 (after first dose)	84
Week 16	113	85	140
Week 24	169	141	196
Week 32, 40,	7*x+1	7x-27	7*x + 28
Safety Follow-up		max (andecaliximab end date, Nivo end date) + 1	max (andecaliximab end date + 30 days, Nivo end date + 5 months)

Table 4. Analysis Visit Windows for Tumor Assessments

Analysis Visit	Nominal Study Day	Lower Limit (inclusive)	Upper Limit (inclusive)
Baseline	-28	Randomization date - 60	Randomization date
Week 8	57	1	84
Week 8 confirmatory	Day of Week 8 visit + 28	Day of Week 8 visit + 28	
Week 16	113	85	140
Week 16 confirmatory	Day of Week 16 visit + 28	Day of Week 16 visit + 28	
Week 24	169	141	196
Week 24 confirmatory	Day of Week 24 visit + 28	Day of Week 24 visit + 28	
Week X=32, 40, ...	$7*x+1$	$7x-27$	$7*x + 28$

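### SAP 6.2.1 sets the PFS and DOR censoring date at the last adequate scan without requiring that scan to precede the missed scans or the new therapy

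*SAP*

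**What the plan says.** SAP 6.2.1 gives a single censoring date: "Data will be censored on the date of last adequate tumor assessment for subjects (including assessments with a NE outcome"). Three groups follow. The first is subjects with neither definitive progression nor death before they leave the study. The second is those "who start new anticancer therapy prior (radiation therapy excluded) to definitive PD or death". The third is those "who have ≥ 2 consecutive missing tumor assessments before definitive PD or death". SAP 6.2.3 applies the same rules to DOR.

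The only fallback concerns baseline: "Subjects without any adequate baseline tumor assessment are censored on the randomization date". Adequacy is then fixed by date: "The adequate baseline tumor assessment is defined as the window from (randomization date - 35 days) to randomization date". Table 4 in SAP 3.8.2 uses a different lower limit for the baseline scan, "Randomization date - 60".

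Protocol 8.3 is more specific, for PFS and DOR alike:
- Survivors without progression are censored at the earlier of the start of other antitumor treatment and the last objective documentation of no progression.
- Subjects who progress or die after two or more consecutive missing or inadequate assessments "will be censored at the last time prior to the missing assessments that lack of definitive disease progression was objectively documented".

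**The concern.** The SAP's three conditions select subjects. They do not limit which assessment supplies the date. Read as written, a subject who misses two scans and then returns is censored at a scan after the gap, and a subject who starts other treatment can be censored at a scan taken on that treatment. Both contradict protocol 8.3. Compared with the protocol, the subject stays in the risk set, event-free, through time that was unobserved or spent on other treatment, which pushes the Kaplan-Meier curve up.

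The SAP also accepts non-evaluable scans as censoring dates. The protocol requires documented absence of progression and groups inadequate scans with missing ones.

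There is a separate gap. The fallback to randomization covers only subjects without an adequate baseline scan. A subject who has one, but no later scan and no event, is censored before randomization. A negative time is invalid in a survival analysis, and it also enters the PFS follow-up summary, which uses the censoring date for subjects who have stopped tumor assessment.

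**Working it through.** The plan states no figure that depends on this rule, so there is none to reproduce. I applied the SAP's own formulas to constructed scan histories.

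**Inputs**
- PFS in months = (censoring date - randomization date + 1) / 30.4375 (SAP 6.2.1). DOR is the same with the first-response date (SAP 6.2.3).
- Scans every 8 weeks (Protocol 6.2.9.2). I take Week w as 7w days after randomization, that is, first dose on the day of randomization.
- A further scan "at the EOS visit if one has not been performed within the last 8 weeks" (Protocol 6.2.9.2). Starting other antineoplastic therapy is a reason to end study participation (Protocol 3.7), which leads to the EOS assessments (Protocol 6.6).
- Screening scan up to 28 days before randomization (Protocol 6.2.9.2); adequate up to 35 days before (SAP 6.2.1).

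**1. Missed scans, PFS.** Stable at Week 8, Weeks 16 and 24 missed, stable at Week 32, progression at Week 40.
- Protocol, Week 8: (56 + 1) / 30.4375 = 1.87 months.
- SAP wording, Week 32: (224 + 1) / 30.4375 = 7.39 months, later by 168 / 30.4375 = 5.5 months.
- SAP wording if the progression scan itself counts as adequate, Week 40: (280 + 1) / 30.4375 = 9.23 months, later by 224 / 30.4375 = 7.4 months.

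This applies both rules to any earlier gap. If the gap must run up to the progression, let the Week 32 scan be non-evaluable instead. Taking such a scan as inadequate in the protocol's sense, the gap covers Weeks 16 to 32 and the protocol still censors at Week 8. The SAP accepts the scan and still censors at Week 32. The same 1.87 and 7.39 months result.

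**2. Missed scans, DOR.** First response at Week 16, Weeks 24 and 32 missed, stable at Week 40, progression at Week 48.
- Protocol, Week 16: (112 - 112 + 1) / 30.4375 = 0.03 months.
- SAP wording, Week 40: (280 - 112 + 1) / 30.4375 = 5.55 months.

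**3. New therapy.** Last scan on day 56, other therapy from day 110, EOS scan without progression on day 117 (61 days after the last scan, so it is due).
- Protocol, earlier of day 110 and day 117: (110 + 1) / 30.4375 = 3.65 months.
- SAP wording, day 117: (117 + 1) / 30.4375 = 3.88 months, 7 days after the therapy began.
- Last scan before the therapy, day 56: 1.87 months. This is a third answer and matches neither document.

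**4. Baseline scan only, no event, PFS.**
- Scan 28 days before randomization: (-28 + 1) / 30.4375 = -0.89 months.
- Scan 35 days before: (-35 + 1) / 30.4375 = -1.12 months.
- The result is negative for any scan two or more days before randomization.

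**5. Why DOR needs its own floor.** A scan 36 to 60 days before randomization is a baseline scan in Table 4 but not adequate in 6.2.1, so the subject is censored at randomization. With a response at Week 8, DOR = (0 - 56 + 1) / 30.4375 = -1.81 months.

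**The case against.** The best defence is that any statistician would supply the missing words. SAP 6.2.1 imputes a year-only start date of new therapy to no earlier than the end of the month of a same-year last adequate assessment, which suggests that a scan before the therapy was meant. Adequate is not defined for post-baseline scans, so it might exclude a progression scan or the baseline scan. This is fair evidence of intent, but it does not settle the dates. SAP 6.1 does write the cut-offs, excluding assessments after new therapy or after two missed scans, and it writes them for ORR only.

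Two further points stand and limit the finding:
- Protocol 6.2.9.2 stops scheduled imaging at the start of new anticancer treatment, so scans after it should be few, and the constructed case differs by only 7 days.
- This is the follow-up SAP. PFS and DOR are secondary, p-values are for display only (SAP 2.3 and 6), and efficacy in the CSR comes from the primary analysis under a separate SAP that is not among the documents (SAP 1 and 6).

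A reader might infer more than the documents support:
- That negative PFS times breach the protocol. They do not, because protocol 8.3 has no floor at randomization either.
- That DOR censoring can precede randomization. It cannot, because a responder has a post-baseline scan and the only fallback is randomization itself. It can precede the first response.
- That the comparison between arms is biased. No count of affected subjects is given, and nothing shows that they would fall unevenly.

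**Conclusion.** The rule is wrong as written and should be corrected. The missed-scan condition contradicts protocol 8.3. In the constructed history it moves the PFS censoring date by 5.5 months, or 7.4 if the progression scan counts as adequate. The new-therapy limit is also unwritten, with a small expected effect. The negative PFS time for baseline-only subjects is a gap in the SAP, not a conflict between the documents.

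These sizes are for single constructed subjects and rest on a literal reading of 6.2.1. They are not estimates of a shift in median PFS or in the hazard ratio. The effect is confined to secondary endpoints in the follow-up analysis. Whether the primary-analysis SAP carries the same wording cannot be seen, so nothing can be concluded about the efficacy results in the CSR.

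**What to change.** Replace the single censoring sentence in SAP 6.2.1 with a rule for each case:
- **Two or more consecutive missing or inadequate assessments before progression or death:** censor at the last evaluable (not NE) assessment without definitive progression before the first missed or inadequate one.
- **New anticancer therapy:** choose one rule and state it. Either follow protocol 8.3 (the earlier of therapy start and last documented non-progression), or use the last evaluable assessment before the therapy and declare this as a change from the protocol. Say also how progression or death after new therapy is handled: the SAP censors such subjects, while the protocol's new-therapy clause names only survivors without progression.
- **No evaluable post-baseline assessment and no event:** censor PFS at randomization.
- **DOR:** apply the same limits, with the first-response date as the floor.

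Reconcile the 35-day and 60-day baseline windows at the same time. The cost is a few lines of SAP text and derivation code, with no new data. The missed-scan limit restores the protocol rule. The randomization floor is an addition to it, and the new-therapy limit restores it only if the first option is chosen.
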